The Innocor device has the ability to measure cardiac output by mixing in small amounts of Nitrous Oxide (N₂O) and Sulfur Hexafluoride 6 (SF₆). Oxygen consumption is measured by the Innocor device without the addition of these gases. For this study N₂O and SF₆ will not be used. No part of the Innocor device will be attached to the skin for the purposes of this research. The Innocor device can be used to measure pulmonary function tests requiring some degree of cooperation from subjects. It is possible to obtain measurements of oxygen consumption using the Innocor device in intubated, sedated patients without their cooperation. For non-intubated patients, they would only need to be able to follow the direction to breathe out through the sensor. No timing of breaths are required.

Protocol for Healthy Adult Volunteers

After obtaining a written informed consent from the volunteer, the subject will be randomized using pre-prepared opaque sealed envelopes to which medication (albuterol or levalbuterol) they receive first. The measurements will be obtained over 2 consecutive days. The dosage of

Albuterol will be 5 mg mixed with 2 to 3 ml of saline and will be aerosolized over 10 minutes. The dosage of levalbuterol will be 1.25 mg mixed with 2 to 3 ml of saline and will be aerosolized over 10 minutes. On day 1 of the study the patient will receive the medication they were randomized to. At approximately the same time of day on day 2 the subject will receive the other medication. Following each breathing treatment, oxygen consumption will be measured using the non-invasive Innocor machine. Oxygen consumption will be measured at baseline and then following the medication at times 0, 5 min, 10, 20, 40 and 60 minutes. Temperature will be measured prior to the aerosolized medication and heart rate, blood pressure, oxygen saturations, and respiratory rate will be measured at intervals over the 60 minutes of oxygen consumption measurement.

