Study participants will be given a questionnaire at the end of each intervention. Oxygen consumption is dependent on many variables such as body temperature, amount of physical activity, amount of caffeine consumed and if they experience any effects such as nausea, palpitations, tremors or jitteriness. Collecting additional information for these confounders will be crucial in analyzing the final outcomes on the two groups with regards to change in oxygen consumption from baseline. The volunteers will also be asked if they have used albuterol or levalbuterol in the past. Albuterol is known to cause various effects such as nausea, palpitations, and tremors or jitteriness and knowledge about these side effects will help the physicians choose the most appropriate treatment for the subject.

G. Statistical considerations

There is no published information on the increase in oxygen consumption caused by L-Albuterol in humans. Animal studies show oxygen consumption increases from a baseline of 4.8 ± 0.3 ml/kg/min ([name] 1991) to 7.0 ± 0.3 ml/kg/min following L-Albuterol administration. This was an increase in oxygen consumption of 46%. Unpublished pilot data in rhesus monkeys suggests oxygen consumption increases from a baseline of 5.0 ± 0.6 ml/kg/min to 5.26 ± 0.8 ml/kg/min. However, differences in

sedation compared to previous animal studies resulted in greater variability in the measurement of oxygen consumption. We expect racemic albuterol will be associated with a smaller increase in oxygen consumption compared to L-Albuterol. A clinically significant difference in oxygen consumption might be as little as 10% in a child who is critically ill. We will use a paired t-test to compare mean difference in oxygen consumption between L-Albuterol and racemic albuterol in children. Using a paired difference to be detected of 10%, expected standard deviation of 20%, power of 0.9 and significance level (alpha) of 0.05 we calculated a sample size of 44 patients for this study. Given the possibility of drop out or incomplete data collection we anticipate approaching 50 patients to complete the study. Given we cannot be certain that the degree of variability will remain the same across the three cohorts we will target recruitment to 50 subjects in each cohort. We will perform an interim analysis after the first 20 patients are recruited.

References:

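### Known non-drug drivers of oxygen consumption are mostly asked about after each session, not standardised in volunteers or charted in patients

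*Combined protocol and SAP*

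**What the plan says.** The last paragraph of section F lists temperature, activity, caffeine and several symptoms as things that VO2 depends on or that accompany it, and calls data on these confounders crucial. The instrument is a form: "Study participants will be given a questionnaire at the end of each intervention". The form itself is not in the documents, and its list of topics is open-ended.

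For volunteers, the Protocol for Healthy Adult Volunteers adds a temperature before the aerosol, vital signs over the 60 minutes, and a second session at about the same hour on the next day. It sets no rule on caffeine, food, activity or rest beforehand.

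For patients, the corresponding section sets a baseline VO2, readings up to 60 minutes, a gap of at least 4 hours between drugs, and a second day in reversed order. It notes: "It is possible to obtain measurements of oxygen consumption using the Innocor device in intubated, sedated patients without their cooperation". Intubated patients are eligible from 1 month of age. The secondary objectives in section D list minute ventilation, respiratory rate, heart rate, blood pressure and oximetry with each intervention.

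Section G says that in the animal pilot differences in "sedation compared to previous animal studies resulted in greater variability in the measurement of oxygen consumption". The only analysis it names is a paired t-test, without covariates.

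**The concern.** The plan identifies influences on its own endpoint and then, for the most part, neither holds them steady nor measures them when VO2 is read.

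- **Volunteers.** One drug is given per day. Someone may drink coffee, eat or walk in briskly before one session and not the other. A question afterwards records this, at best, once it is too late to prevent it, and no use of the answer is specified.
- **Patients.** A sedated or infant patient cannot fill in a form, and no proxy or chart version is described. Sedation is the one factor that the plan itself links to extra VO2 variability, yet no section asks for a sedation or ventilator record.

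At stake is how clearly a 10% difference between drugs can be seen, and whether an odd session can be understood later. If peak VO2 means the highest post-dose reading (the plan does not define it), one disturbed reading could set a session's value.

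**Working it through.** **1. The plan's sample size.** Inputs, all from section G: a 10% difference ("Using a paired difference to be detected of 10", in per cent), a 20% standard deviation ("expected standard deviation of 20", in per cent, read as the SD of the paired difference), and "power of 0.9 and significance level (alpha) of 0.05". Sidedness is not stated.

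- Normal approximation, two-sided: ((1.960 + 1.282) × 20/10)² = 42.03, so 43.
- Noncentral t, two-sided, effect 10/20 = 0.5: the smallest n with power of at least 0.90 is 44 (power 0.9000).
- Noncentral t, one-sided: 36, which does not match.

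The plan's statement, "we calculated a sample size of 44 patients for this study", is therefore reproduced. The target of 50 per cohort fits a 12% loss: 44/0.88 = 50. Power with 50 complete pairs is 93.4%.

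**2. The sedation remark in figures.** Reading the ± values in section G as SDs (an assumption), the coefficients of variation before and after drug are:

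- earlier animal study: 0.3/4.8 = 6.3% and 0.3/7.0 = 4.3%;
- pilot: 0.6/5.0 = 12.0% and 0.8/5.26 = 15.2%.

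The pilot's relative spread is about 2 to 3.5 times larger. The plan attributes this to sedation differing between studies. It does not describe sedation drifting within a session.

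**3. Does the 20% planning SD already allow for spread of that size?** It may. The within-subject correlation ρ is not given, so it is an assumption here.

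- Pilot before-after difference: √(0.6² + 0.8² − 2ρ × 0.6 × 0.8)/5.0 is 20.0% at ρ = 0 and 14.4% at ρ = 0.5.
- Two post-dose values, each with the pilot's post-dose SD: √(2(1 − ρ)) × 0.8/5.26 is 21.5% at ρ = 0 and 15.2% at ρ = 0.5.

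If the t-test compares changes from baseline, the SD depends on correlations among four readings, which the documents do not give.

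**4. What the design removes.** Stable differences between people cancel in the paired difference. A disturbance specific to one session does not. If disturbances are unrelated to drug, they add variance but have mean zero in the comparison. If they came on top of the 20%, SD = √(20² + extra²). The extra SDs below are illustrative and are not in the documents.

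| Extra SD | Total SD | n for 90% power | Power at 44 | Power at 50 |
|---|---|---|---|---|
| 0% | 20.0% | 44 | 90.0% | 93.4% |
| 10% | 22.4% | 55 | 82.6% | 87.3% |
| 15% | 25.0% | 68 | 73.7% | 79.2% |
| 20% | 28.3% | 87 | 63.0% | 68.8% |

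If the 20% already contains this noise, only the first row applies, and controlling the noise would be a gain in precision.

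**5. What is captured, by cohort.**

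| Item | Volunteers | Patients |
|---|---|---|
| Temperature | measured before dosing | no measurement specified |
| Activity, caffeine | asked afterwards | asked afterwards, if able to answer |
| Food | not mentioned | not mentioned |
| Sedation, ventilator settings | not applicable | no record specified |
| Heart and respiratory rate, blood pressure, oximetry | at intervals over 60 minutes | secondary objective |
| Time of day | matched | not matched; drug order reversed on day 2 |

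**The case against.** The best defence is that the questionnaire does not stand alone. Volunteers have a measured temperature, vital signs and a matched hour. Every session has a baseline VO2, order is randomised, and patients repeat both drugs in reverse order. Minute ventilation and respiratory rate are collected. ICU charts probably hold temperature, sedation and ventilator data already, so little need be lost for good. Non-intubated patients must be able to manage a mouthpiece, so the infant point concerns the intubated cohort, and caffeine and exercise hardly matter in a sedated child.

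Most of this stands, and it limits the point to precision and data capture. It does not remove it. Baseline and crossover leave changes within and between sessions untouched. Minute ventilation cannot show whether a rise came from the drug or from a changed setting. Retrieving chart data later is possible only as far as entries line up with the VO2 readings, and the plan specifies no such extraction. Because the form is not shown, all that can be said about sedation is that no section mentions recording it.

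Several stronger readings are tempting, and the documents do not support them.

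- **That the comparison is biased.** Randomised order makes session disturbances mainly noise. The study is open label, so staff could alter sedation or support knowing the drug, but nothing shows that this would favour either drug. A record is what would allow a check.
- **That sedation explains the gap between the 46% animal rise (7.0/4.8 − 1) and the pilot's 5.2% (5.26/5.0 − 1).** The plan blames sedation for variability, not for the mean. Section G does not name the pilot drug, and the background credits a 46.5% rise to racemic albuterol where section G says L-Albuterol.
- **That a ventilator change alone can match the 10% target**, because the background puts the oxygen cost of breathing at 8% to 24% of VO2. That figure is the whole step between spontaneous and mechanically ventilated breathing, in 13 patients. An ordinary adjustment would move only some fraction of it.

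**Conclusion.** The point holds as a gap in standardisation and data capture. Volunteers' caffeine, food and activity are free to differ between days. For patients, no temperature, sedation or ventilator record is specified, and the instrument offered cannot be answered by those who are sedated or very young. No section says how any confounder data would enter the analysis.

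Its size cannot be fixed from the documents. The sample size is arithmetically sound, and the 20% SD may already include variability of the pilot's size, so a loss of power is not shown. The lower rows of the power table apply only if extra session noise comes on top of that 20%. The change is worth making because it is cheap and because readings without a matching bedside record are harder to interpret afterwards.

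**What to change.** 1. **Volunteers.** In the Protocol for Healthy Adult Volunteers, require the same preparation for both sessions: no caffeine beforehand, the same fasting interval, a fixed seated rest before baseline, and seated until the 60-minute reading. The investigators set the exact durations.
2. **Patients.** Replace the self-report confounder items with chart items noted at baseline and at each VO2 reading: temperature, sedation score and infusions, ventilator mode and support, and feeding. These are observations only; no clinical setting is changed for the study.
3. **Analysis.** Keep every session in the primary analysis. Flag sessions in which sedation or ventilator support changed between baseline and 60 minutes, and pre-specify a sensitivity analysis that leaves them out. State the caveat that such changes may be consequences of the drug, so that exclusion selects on a post-treatment event and breaks pairs.
4. **Symptoms.** Do not adjust for nausea, palpitations, tremor or jitteriness. The questionnaire paragraph lists them among the confounders but also describes them as effects of albuterol, so adjustment could remove part of the drug effect. Report them as outcomes.

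The cost is an instruction sheet and minor burden for volunteers, and a few extra data fields for patients.

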After obtaining a written informed consent from patients/guardians that are scheduled to receive albuterol or levalbuterol, the subjects will be randomized using pre-prepared opaque sealed envelopes to two different groups, group A and B. The measurements will be done over 2 separate days. On Day 1 Group A will receive albuterol first followed by levalbuterol for when the next dose is due. On day 2 the order will be reversed and therefore levalbuterol will be given first followed by albuterol. Group B will be first given levalbuterol followed by albuterol for the next scheduled dose. If the patient is receiving albuterol as their clinically prescribed medication the levalbuterol dose will be chosen to be ½ that milligram amount. If the patient is receiving levalbuterol as their clinically prescribed medication the albuterol dose will be chosen to be 2 times that milligram amount. Typical dosages in the ICU would be albuterol 0.15 mg/kg with a minimum of 2.5 mg and maximum of 5 mg and levalbuterol 0.63 mg and 1.25 mg respectively. However, if a young child is clinically prescribed a dose of Albuterol of 1.25 mg(max dose of levalbuterol) then the dose of Levalbuterol for the study would be 0.63 mg. Albuterol is only FDA approved for marketing to patients greater than 2 years of age but it has been used clinically at all age levels. Likewise, Levalbuterol has been used clinically in infants and children but is only FDA approved for marketing to patients greater than 6 years of age. Measurements of oxygen consumption will be done using the non-invasive device Innocor. This device has been validated for measurement of oxygen consumption against the gold standard Douglas bag. Oxygen consumption will be measured at baseline and then after giving albuterol and levalbuterol at times 0, 5 min, 10, 20, 40 and 60 minutes. The two medications will be given at least 4 hours apart.

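### Drug order is randomised but no stated analysis uses it: no test is named for the adult volunteers, and the paired t-test named for children has no period term

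*Combined protocol and SAP*

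**What the plan says.** All references are to the combined protocol and SAP.

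- **Volunteers** (section F, Protocol for Healthy Adult Volunteers). Each volunteer is "randomized using pre-prepared opaque sealed envelopes to which medication (albuterol or levalbuterol) they receive first". The second drug follows a day later: "At approximately the same time of day on day 2 the subject will receive the other medication". Oxygen consumption is measured at baseline and at set times up to 60 minutes after dosing.
- **Patients** (section F, Protocol for intubated and non-intubated patients). Envelopes assign Group A or Group B, and both drugs are given on each of two days. After Group A's day 1 the text reads "On day 2 the order will be reversed and therefore levalbuterol will be given first followed by albuterol". For the other group it says "Group B will be first given levalbuterol followed by albuterol for the next scheduled dose", and it does not spell out that group's day 2.
- **Analysis** (section G). The only named test is in the sentence "We will use a paired t-test to compare mean difference in oxygen consumption between L-Albuterol and racemic albuterol in children". For size, "we will target recruitment to 50 subjects in each cohort", and healthy adults are one of the three cohorts.
- **Other analysis remark** (questionnaire paragraph just before section G). It speaks of change in oxygen consumption from baseline, and says of factors such as temperature, activity, caffeine and symptoms: "Collecting additional information for these confounders will be crucial in analyzing the final outcomes on the two groups". It then adds: "Albuterol is known to cause various effects such as nausea, palpitations, and tremors or jitteriness".

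No period, sequence or order term appears anywhere. No allocation ratio or blocking is stated for the envelopes.

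**The concern.** In a crossover, a subject's drug difference contains the drug effect plus or minus any shift between the first and second session, with the sign set by the order received. Randomising order makes that shift separable from the drug effect, but only if the analysis uses the order. A paired t-test pools all differences. The shift then inflates the error term and, if more subjects received one order than the other, part of it stays in the estimate.

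The exposure differs by cohort. A volunteer has one pair, and so has a patient who completes one day only. A patient who completes both days in reversed order has two pairs in which a constant within-day shift has opposite signs, so it cancels in that patient's mean.

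At stake are precision and, with unequal order groups, some bias in the volunteer comparison and in incomplete patient data. As written, the volunteer comparison also has no named test, which leaves the choice until after the data are seen.

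**Working it through.** **Inputs.** From section G: difference 10%, SD 20%, power 0.9, alpha 0.05, 44 patients, target 50 per cohort. Two readings are assumed because they reproduce the plan's figure: the SD is that of the within-subject difference, and the test is two-sided. The session shift s (first minus second session, in percentage points) is not in the documents, so every value of s is an assumption.

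**1. The plan's own figure.** Paired t-test, noncentral t, df = n − 1, noncentrality = (10/20)√n. The smallest n with power 0.90 is 44 (power 0.9000). At n = 50 power is 0.9339. The stated 44 is correct.

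**2. Model for one pair per subject.** D = δ + s in one order group and δ − s in the other, plus error with SD 20.

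- Paired t-test: the expected estimate is δ + s(n₁ − n₂)/n. With equal groups the variance of D is about 20² + s².
- Period-adjusted: the estimate is the average of the two order-group means, so s drops out. SE = (20/2)√(1/n₁ + 1/n₂), df = n − 2.

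**3. Equal order groups** (simulation, 200,000 trials per cell):

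| s | n = 44, paired t | n = 44, adjusted | n = 50, paired t | n = 50, adjusted |
|---|---|---|---|---|
| 5 | 0.89 | 0.90 | 0.93 | 0.93 |
| 10 | 0.85 | 0.90 | 0.90 | 0.93 |
| 15 | 0.78 | 0.90 | 0.84 | 0.93 |
| 20 | 0.67 | 0.90 | 0.75 | 0.93 |

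Unrounded at s = 5, the loss is 0.888 against 0.900 (n = 44) and 0.926 against 0.934 (n = 50). At s = 3 and n = 50 it is about 0.003. At s = 10 the mean 95% CI half-width is 6.3 points against 5.7 (n = 50), and the paired t-test's type I error is 2.9%. With equal groups the test is therefore conservative.

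**4. Unequal order groups, s = 10.**

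- 20/30: bias = 10 × (30 − 20)/50 = 2.0 points; type I error 7.0%.
- 17/27: bias = 10 × (27 − 17)/44 = 2.3 points; type I error 7.7%.
- 19/25: bias = 10 × 6/44 = 1.4 points; type I error 4.5%, still conservative.
- With period modelled: bias 0 and type I error 5.0% throughout.
- At 20/30 with a true difference of 10, if the shift works against the drug difference, power is 0.72 unadjusted and 0.92 adjusted. If it works in favour, the estimate averages 12.0.

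If the envelopes follow simple allocation (an assumption), a split of 20/30 or worse has probability 0.20 at n = 50, and 17/27 or worse has probability 0.17 at n = 44.

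**5. Averaged over simple allocation, s = 10.** Type I error is 5.0% for both methods. Power is 0.83 against 0.89 (n = 44) and 0.87 against 0.93 (n = 50).

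**6. If the 20% SD already contains the shift.** At s = 10 both methods exceed 0.90: 0.93 against 0.96 (n = 44) and 0.96 against 0.98 (n = 50).

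**7. Patients with two reversed days.** Day 1 gives δ + s and day 2 gives δ − s, so the mean is δ. With an assumed between-day correlation of 0.5, s = 10 and n = 44, a t-test on the two-day mean has power 0.963 and type I error 0.050. If day 2 is missing in 25% or 50% of patients, power on available-day means is 0.935 or 0.905. Adding a period term to those means gives 0.946 or 0.929.

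**The case against.** **The test is worded for children.** This stands. The plan assigns no paired t-test to volunteers, so there is nothing there to replace. The gap is that no test is named for them. For children, most of the risk falls on those who complete one day only, and the documents do not say how many that will be.

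**The design already controls session differences.** A reader might infer that nothing in a volunteer's data offsets a day-to-day shift. The documents do not support that. Each treatment has its own baseline, time of day is held roughly constant, and the questionnaire paragraph refers to change from baseline. If change from each session's baseline is analysed, an additive shift in level cancels. A shift in the response to dosing remains, as does a shift in post-dose values if change is not used. Section G does not settle which outcome is compared.

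**The shifts are assumed, and 10 points equals the whole effect sought.** This also stands. At small shifts the loss is negligible.

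**The type I errors of 7% depend on particular splits.** This is correct. They need a sizeable shift and an uneven split together, and the average over simple allocation is 5.0%. A reader might infer general inflation of false positives; the figures do not show it.

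**Adjustment costs more than one degree of freedom when groups are unequal.** This is correct, and the cost is counted below.

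**The side issues are small.** The reversal on day 2 is naturally read as applying to both groups, and no covariate model is specified, so adjustment for symptoms is an inference from the remark about confounders. Both points need only clarification.

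**Conclusion.** The point holds in a limited form and merits a change to the plan. Order is randomised but enters no stated analysis, and the volunteers have no named test. For single-pair subjects, any session shift that baseline subtraction does not remove lowers precision, and it biases the estimate when order groups are unequal. At an assumed 10-point shift and n = 50 the size is 0.90 against 0.93 in power with equal groups, or 2.0 points of bias and about 7% type I error at 20/30. At 5 points or less with equal groups it is about 0.01 in power or less.

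This rests on a shift the documents do not give, on 20% being the SD of the difference before any shift, and on one pair per subject. It does not show that the trial is invalid or that 44 is wrong. Patients who complete both days in reversed order are protected against a constant shift, provided that both groups reverse and one mean difference per patient is analysed. A period term does not remove carry-over.

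**What to change.** In section G:

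1. **Volunteers:** name a period-adjusted crossover analysis (drug and period, subject as the pairing unit) of change from each session's own baseline.
2. **Patients:** analyse one mean drug difference per patient over the two reversed days. When a day is missing for some patients, use a model with drug, period and a patient-level random effect on the drug difference. Do not count a patient's two daily pairs as independent.
3. **Covariates:** if any are used, restrict them to values fixed before dosing. Do not adjust for nausea, palpitations, tremors or jitteriness, which the protocol itself describes as drug effects.

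In section F, reconcile the patient protocol wording so that Group B's day-2 order is explicit.

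**Cost.** A few sentences, and no data beyond the order each subject received. With equal groups, one degree of freedom takes power from 0.9339 to 0.9337 at n = 50 and from 0.9000 to 0.8997 at n = 44. With unequal groups the variance also rises by the factor (n/4)(1/n₁ + 1/n₂). At 20/30 this is 12.5 × 0.0833 = 1.04, with adjusted power 0.924; at 17/27 it is 11 × 0.0959 = 1.05, with adjusted power 0.884. With no shift, the unadjusted test would have 0.934 and 0.900. N = 44 and the target of 50 per cohort can stay.

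### The only named test, a paired t-test, leaves the pre-dose VO2 readings of the volunteer cohort unused or merely subtracted; adjusting for them would be a nearly free, optional gain in precision

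*Combined protocol and SAP*

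**What the plan says.** Section G (Statistical considerations) gives the whole analysis in one sentence: "We will use a paired t-test to compare mean difference in oxygen consumption between L-Albuterol and racemic albuterol in children". It does not say whether the quantity compared is post-dose VO2, change or percent change, and it names no covariate and no period term. The sentence refers to children. Section F also has a cohort of healthy adult volunteers, for whom no separate test is given.

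The sample-size inputs follow: "Using a paired difference to be detected of 10" percent, "expected standard deviation of 20" percent, "power of 0.9 and significance level (alpha) of 0.05". From these, "we calculated a sample size of 44 patients for this study". Section G then says "we will target recruitment to 50 subjects in each cohort".

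The Protocol for Healthy Adult Volunteers (section F) has one drug on each of two consecutive days, in randomized order. It states: "Oxygen consumption will be measured at baseline and then following the medication", with six post-dose times up to 60 minutes. The questionnaire paragraph at the end of section F lists body temperature, physical activity and caffeine as influences on VO2, and speaks of analysing outcomes "with regards to change in oxygen consumption from baseline". No model is given that uses either the baseline or these factors.

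**The concern.** Temperature, activity and caffeine can differ between a volunteer's two days. A pre-dose VO2 on each day captures their combined effect on that day. A paired t-test can treat this reading in only two ways. Applied to post-dose values, it ignores the reading (slope fixed at 0). Applied to change from baseline, it subtracts the reading in full (slope fixed at 1). Percent change is roughly subtraction on the log scale.

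Neither fixed slope is generally best. Ignoring the baseline leaves removable day-to-day variation in the drug contrast. Subtracting it adds noise when pre-dose and post-dose differences are only modestly correlated. What is at stake is the width of the confidence interval for the volunteer contrast, from data the plan already collects.

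**Working it through.** **Inputs from section G.** Difference 10%, SD 20%, power 0.90, alpha 0.05 (sidedness not stated), calculated n 44, target 50 per cohort.

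**Assumed, because the documents do not give it.** ρ, the correlation across subjects between the pre-dose and post-dose within-subject drug differences, and equal variances σ² of those two differences.

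**1. The plan's own figure.** Normal approximation, two-sided: n = [20 × (1.960 + 1.282) / 10]² = 42.03, so 43. With the noncentral t, n = 44 gives power 0.900. A one-sided test gives 36 and does not match. The stated 44 is therefore correct for a two-sided paired t-test. At n = 50 the power is 0.934.

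**2. Variance of the drug contrast per subject.**
- Baseline ignored: σ²
- Baseline subtracted: 2(1−ρ)σ²
- Baseline as covariate: (1−ρ²)σ²

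The covariate analysis therefore has variance ratio 1−ρ² against ignoring and (1−ρ²)/[2(1−ρ)] = (1+ρ)/2 against subtracting. At ρ = 0.5 both ratios are 0.75. For non-negative ρ that 25% reduction is the largest possible gain over the better of the two t-tests.

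**3. Cost of estimating the slope.** Variance is multiplied by (n−2)/(n−3) and one degree of freedom is lost. At n = 44 and ρ = 0.5 the effective SD is 20 × √0.75 × √(42/41) = 17.53.

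**4. If the 20% SD is for post-dose differences (baseline ignored).**

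| ρ | Power n=44, t-test | Power n=44, adjusted | Power n=50, t-test | Power n=50, adjusted | n for 0.90, adjusted |
|---|---|---|---|---|---|
| 0 | 0.900 | 0.893 | 0.934 | 0.929 | 46 |
| 0.3 | 0.900 | 0.919 | 0.934 | 0.949 | 42 |
| 0.5 | 0.900 | 0.959 | 0.934 | 0.977 | 35 |
| 0.7 | 0.900 | 0.994 | 0.934 | 0.998 | 25 |

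**5. If the 20% SD is for change-score differences (baseline subtracted).** Adjusted SD = 20 × √[(1+ρ)/2].

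| ρ | Adjusted SD | n for 0.90, t-test | n for 0.90, adjusted |
|---|---|---|---|
| 0.3 | 16.12% | 44 | 31 |
| 0.5 | 17.32% | 44 | 35 |
| 0.7 | 18.44% | 44 | 39 |
| 0.9 | 19.49% | 44 | 43 |

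**6. Where the gain stops.** Against ignoring, break-even is ρ² = 1/(n−2), so ρ ≈ 0.15 at n = 44 (0.14 at n = 50). Against subtracting, it is ρ = 2(n−3)/(n−2) − 1, so about 0.95 at n = 44 (0.96 at n = 50).

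**7. Simulation check.** With 20,000 trials at n = 50, the standard errors for ignore / subtract / adjust were 2.87 for adjust against 2.84 and 3.97 at ρ = 0. At ρ = 0.5 they were 2.82 / 2.82 / 2.47, and at ρ = 0.9 they were 2.84 / 1.27 / 1.25. This agrees with the formulas.

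**8. Period term.** It costs one further degree of freedom. With variance factor (n−3)/(n−4), power at n = 44 and ρ = 0.5 is 0.958 instead of 0.959, and 31, 35 and 39 do not change.

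**The case against.** The strongest reply is that nothing here is invalid. A paired t-test in a randomized crossover is a sound analysis, the sample size is right on its inputs, and ρ is unknown, so the gain could be negligible. All of that stands, and it keeps the point optional.

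Two stronger readings are tempting, and the documents do not support them.

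- *That power is lost on the primary contrast.* The primary objective (section D, Study Objectives) concerns patients in the two intensive care units. The clearest case for a separate pre-dose reading per drug is the volunteer cohort. Patients receive both drugs on each day, and section F does not say that each dose has its own baseline. A baseline shared by both drugs cancels from the difference and offers no gain.
- *That the stated 0.90 power will be missed.* Suppose the 20% were the SD of raw post-dose differences while change scores were tested. At ρ = 0.3 the SD would then be 20 × √1.4 = 23.7% and power at n = 44 would be 0.78. But that pairs an SD for one outcome with a test on another. If SD and test refer to the same outcome, power is 0.90 at 44 and 0.934 at 50.

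The equal-variance assumption is also open to challenge. Section G's pilot SDs in monkeys, 0.6 before and 0.8 after, are unequal. They are between-animal figures and only indicative. With that ratio (0.75) and ρ = 0.3, the change-score SD is √(20² + 15² − 2 × 0.3 × 20 × 15) = 21.1%, and the 0.78 becomes 0.87 (0.91 at n = 50). The assumption affects comparisons with change scores. The ratio 1−ρ² against ignoring baseline does not depend on it.

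**Conclusion.** The point holds as an optional efficiency gain for the volunteer cohort, with moderate confidence. It alleges no bias and no error in the 44. Under equal variances and ρ between 0.3 and 0.7, the benefit is a power of about 0.92 to 0.99 in place of 0.90 at n = 44, or a requirement of about 31 to 39 subjects in place of 44, depending on which outcome the 20% SD describes. At ρ near 0 with baseline otherwise ignored, or near 1 with baseline otherwise subtracted, there is a trivial loss (0.893 against 0.900 at ρ = 0).

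It rests on three readings. Each volunteer dose has its own pre-dose VO2, which is the natural sense of section F but is not spelled out. The test worded for children is the only candidate for the adults; if it is not meant for them, their analysis is unspecified and the same sentence is needed. Finally, the first day's drug is assumed not to shift the second day's pre-dose reading.

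**What to change.** In section G, for the volunteer cohort:

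- Name the outcome: peak post-dose VO2, in line with section D, on the relative scale in which the 10% and 20% are expressed (log VO2 would serve).
- Regress each volunteer's drug difference in that outcome (albuterol minus levalbuterol) on the difference between the two pre-dose values on the same scale, with a term for randomized order coded +1/−1 to carry the period effect.
- Take the drug effect and its 95% CI from the intercept. Do not centre the pre-dose difference at its sample mean, because the intercept must refer to equal baselines.
- State that VO2 is read before each dose on each day.

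Use the same model in patients only where each dose has its own pre-dose reading.

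The cost is a few lines of text and two degrees of freedom, one for the slope and one for the period term. No new volunteer data are needed and the sample size can stay. The text should be settled before the interim analysis planned after 20 patients, so that the choice of model does not depend on the data.
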